9.4 STATISTICAL ANALYSES

9.4.1 GENERAL APPROACH

Descriptive statistics will be produced to summarize the demographic and clinical characteristics of the two study arms. For continuous variables, means and standard deviations (SD) will be provided, as well as medians and interquartile ranges (IQR). For categorical variables, frequencies and percentages will be provided.

All hypothesis tests will be two-sided, and evaluated at the .05 level of significance. 95% confidence intervals will be provided for inferential tests. Statistical analysis will be performed using SAS software, Version 9.4 (SAS Institute Inc., Cary, NC).

9.4.2 ANALYSIS OF THE PRIMARY EFFICACY ENDPOINT(S)

1. **POSAS observer scale total score.** The primary efficacy endpoint will be the total score of the POSAS observer scale, assessed at the 3-month follow-up visit by two blinded evaluators who will not be involved in the placement of the porcine xenograft. For each patient, scores from the two blinded investigators will be combined by calculating the mean. The POSAS (Patient and Observer Scar Assessment Scale) is a validated assessment tool used for the assessment of all types of scars by professionals and patients [17-19]. The observer scale is comprised of 6 items (vascularity, pigmentation, thickness, relief, pliability, and surface area) scored on a scale from 1("like normal skin") to 10 ("worst scar imaginable"). The total score is calculated as the sum of the six items (range, 6-60). This is a subjective endpoint, given that it is based on the evaluating physician's judgment of each scale item.

All patients will be evaluated by two blinded observers, who will be selected from the other attending physicians and/or resident physicians at the site. However, all patients will not be evaluated by the same set of observers due to differences in physician schedules. Agreement between the blinded evaluators will be assessed using the intraclass correlation coefficient (ICC). The form of the ICC will be the ICC(1,2).

Statistical Analysis: The Mann Whitney U test will be used to compare the two study arms on the primary efficacy endpoint based on the mITT Population defined in Section 9.3. No adjustments for multiplicity will be made because there is only one primary endpoint, and this endpoint will not be evaluated during the planned interim safety analysis.

We will summarize the POSAS observer scale score for the two study arms using the mean (SD), and median (IQR). As a measure of effect size between the porcine xenograft and second intention healing groups, we will calculate the Hodges-Lehmann estimate of the median difference, and corresponding 95% confidence interval. This is equal to the median of all paired differences between observations in the porcine xenograft and second intention healing groups.

9.4.3 ANALYSIS OF THE SECONDARY ENDPOINT(S)

Analysis of all secondary endpoints will be considered exploratory. Thus, the analysis of secondary endpoints is not dependent on findings of the primary endpoint, and no adjustments for multiplicity will be made.

1. **POSAS patient scale total score.** Study participants will complete the POSAS patient scale at the 3month follow-up visit. The POSAS patient scale consists of 6 items assessing patients' subjective opinion of scar quality in terms of pain, itching, color, pliability, thickness, and relief. Each item is scored from 1 (normal pigmentation, no itching, etc.) to 10 ("worst imaginable scar or sensation"). The total score of the POSAS patient scale is calculated as the sum of the six items (range, 6-60).

2. **Healing time.** Healing time will be measured in weeks based on patient's responses to question 1 of the weekly follow-up questionnaire ("Is the wound completely healed (i.e., wound is completely closed with no open areas)?"). For example, a patient who first replies "Yes" to this question on the third weekly follow-up questionnaire will be assigned a healing time of 3 weeks. A more objective measure of healing time would not be feasible given our resources and patient schedule.

3. **Ratio of scare size to initial defect size**. The initial postoperative defect size will be measured by the investigator prior to intervention in terms of length and width using a sterile ruler. Initial defect area will be calculated as length times width. Scar size will be measured in terms of length and width at the 3-month follow-up visit, and scar area will be calculated as length times width. The outcome will be calculated by dividing the scar area by the initial defect area.

4. **Pain score at 1 week following surgery.** Patients' pain scores will be measured based on their response to question 2 of the weekly follow-up questionnaire. Patients will be asked to rate their current pain level at the operative site on a scale from 1 (no pain) to 10 (worst imaginable pain).

5. **Number of weeks with pain score above 1.** Patients' pain scores will be measured based on their response to question 2 of the weekly follow-up questionnaire. Patients will be asked to rate their current pain level at the operative site on a scale from 1 (no pain) to 10 (worst imaginable pain).

The POSAS patient scale, healing time, and number of weeks with pain score above 1 are all subjective endpoints. The ratio of scar size to initial defect size is an objective endpoints.

Statistical Analysis: The Mann Whitney U test will be used to compare the two study arms on each of the secondary endpoints based on the mITT Population defined in Section 9.3.

We will summarize each secondary endpoint for the two study arms using the mean (SD), and median (IQR). As a measure of effect size between the porcine xenograft and second intention healing groups, we will calculate the Hodges-Lehmann estimate of the median difference, and corresponding 95% confidence interval. This is equal to the median of all paired differences between observations in the porcine xenograft and second intention healing groups.

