2.2 BACKGROUND

Porcine xenograft has been used as a barrier to the skin for over 30 years, and due to its wound healing promoting factors, we believe that its use may result in decreased healing time, smaller scar size, better cosmetic outcomes, lower pain levels, and decreased rates of infection and other post-surgical complications.

Upon completion of dermatologic surgery following standard procedures, patients will be randomized into one of two groups (porcine xenograft placement or second intention healing). Weekly follow-up via questionnaires will be conducted as well as a final office visit follow-up at 3 months.

The application of porcine xenograft dressings for wound healing was first studied in 1985, with evidence supporting several benefits when compared to traditional dressings [1]. Subsequent studies have substantiated the use of this dressing for a variety of clinical settings [2,3].

The EZ-DERM[™] porcine xenograft is a biosynthetic dressing made from porcine collagen containing aldehyde crosslinking [1,3]. It has been most commonly applied to the management of 2nd degree burns, both partial-thickness and full-thickness defects [4]. This dressing can be used for two healing purposes, either for primary healing or as an intermediate in the preparation for a skin graft [2].

Compared to other biosynthetic dressings, porcine xenografts afford longer wound adherence and can be stored at room temperature [1]. The xenograft triggers rejection by the surgical defect, increasing local vascularization [5]. It also allows for rapid granulation, a reduced risk of infection, as well as reduced wound-related fluid and thermal losses [6-8]. There is also evidence that the quicker wound healing reduces the frequency of dressings, hospitalization time, pain, and analgesic [9,10].

Several clinical case series have extended the use of porcine xenografts to Mohs Micrographic Surgery (MMS) to facilitate post-operative wound care. Porcine xenograft dressings were determined to be safe, well-tolerated, and able to be applied to a wide anatomical range [3, 11,12].

In addition to biosynthetic dressings, healing via second intention remains an alternative [13,14]. The extremities of elderly patients are a common location for wound granulation. Drawbacks to second intention healing on the extremities include prolonged healing time and extended wound care for the patient [15].

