Block randomization will be used to ensure balance in the number of patients allocated to each treatment group. The randomization schedule will be uploaded to REDCap by a statistician outside of the study team. The PI, who will screen eligible subjects, will not have user rights for the Randomization Setup module within REDCap, and will thus be blinded to which treatment arm is next on the randomization list. Due to the nature of the treatment, it will not be possible to blind the patients. Patients will be asked not to inform the blinded physician observers which treatment they received. The PI will use the "Randomize" button within REDCap to assign patients to porcine xenograft or second intention healing after they have been consented and enrolled in the study.

Prior to intervention the defect size will be measured in terms of length and width using a sterile ruler.

After procedure completion wound care instruction will include daily dressing changes and application of petroleum jelly using a cotton tipped applicator to the wound daily until it is healed.

Weekly questionnaires will be given to the patients by phone or email follow-up. All complications and adverse events would be monitored and recorded for both study groups. Assessment of the scar will be blinded in nature.

The mode of treatment for participants will remain consistent throughout the 3-month period, as both methods are reliable for this type of defect. It is not general practice to place a xenograft on a wound healing by second intention or to remove a xenograft after one has been placed to switch to second intention. Should there be any complications, a modified intention to treat principle, described in Section 9, will be adhered to.

The scars for both study groups will be measured at a single follow up visit after 3 months \pm 1 month, and two blinded investigators will then assess the scar for the primary efficacy endpoint at this time. The blinded evaluators will be other MDs not involved in the study who are working in the dermatology department. The Principle Investigator will speak with the physician to outline what needs to be recorded for each patient. The validated physician observer scar assessment instrument (POSAS) will be used for this purpose. Scar size will consist of a length x width measurement using a ruler.

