8 STUDY ASSESSMENTS AND PROCEDURES

8.1 EFFICACY ASSESSMENTS

The authors will conduct a comparative two-arm study investigating outcomes of second intention healing versus porcine xenograft placement of post-operative Mohs surgery or excision wound defects.

This will be a randomized evaluator blinded study with a prior power analysis. Basic demographic data will be obtained including date of birth, sex, and race. Medical record number will be retained to obtain phone number or address for patient call back should patient not show for their follow-up appointments.

Surgical defects 8 mm in diameter or larger on the lower extremities will be eligible for enrollment. Only patients with one wound will be eligible for enrollment. Primary intention (also known as linear layered) repair is not feasible in many patients with defects on the foot, ankle, or distal extremity as these are sites under high tension and poor circulation. Patients with small post-op defects many also opt not to be sutured via primary intention to avoid physical activity restrictions due to the increased risk of wound dehiscence. When closed via primary intention, a 0.8cm defect results in a scar of greater than or equal to 2.4cm.

Patients will be randomized to either receive a porcine xenograft or allow the wound to granulate via second intention. If primary/linear repair is not an acceptable option, the standard of care at Northwell is to allow the wound to heal on its own via second intention post-operatively. Due to recently published retrospective studies, there is a suggestion that porcine xenografts may be a feasible alternative to second intent healing. Currently, it is the surgeon's (and patient's) choice, after a discussion of risks and benefits of each modality, what is done.

Prior to intervention the defect size will be measured in terms of length and width using a sterile ruler.

After procedure completion wound care instruction will include daily dressing changes and application of petroleum jelly using a cotton tipped applicator to the wound daily until it is healed.

Weekly questionnaires will be given to the patients by phone or email follow-up until 12 weeks postsurgery.

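### Healing time is dated at an unblinded patient's first 'Yes', even when later answers, a rescue record or the 3-month visit show the wound open

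*Combined protocol and SAP*

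**What the plan says.** Healing time is the second of five secondary endpoints. Section 9.4.3 defines it: "Healing time will be measured in weeks based on patient's responses to question 1 of the weekly follow-up questionnaire". The question put to the patient is "Is the wound completely healed (i.e., wound is completely closed with no open areas", and the worked example is that a patient first answering 'Yes' "to this question on the third weekly follow-up questionnaire will be assigned a healing time of 3 weeks". Section 3 gives the same rule. Neither section says what a later 'No' does, and neither links the answer to any examination.

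The plan is open about the limits of the measure. It states that "A more objective measure of healing time would not be feasible given our resources and patient schedule", and later that "The POSAS patient scale, healing time, and number of weeks with pain score above 1 are all subjective endpoints". On blinding, section 4.1 says: "Due to the nature of the treatment, it will not be possible to blind the patients".

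Other parts of the plan bear on closure:

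- Section 8.1: "Weekly questionnaires will be given to the patients by phone or email follow-up until 12 weeks postsurgery". No stop after a 'Yes' is stated. The count of weeks with pain and the weekly bleeding question (section 9.4.4) both presuppose that the questionnaires continue.
- Section 4.1: two blinded physicians see the site at 3 months ± 1 month. Section 6.5.1 says POSAS cannot be given on a wound that is not fully healed, so closure has to be judged in practice.
- Section 6.5.1: use of rescue medication is dated in REDCap. Section 9.3 keeps rescued patients in the mITT population once the primary endpoint has been assessed on a healed wound, and that population is used for healing time.

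The analysis is a two-sided Mann-Whitney test at .05, with a Hodges-Lehmann estimate and 95% confidence interval. Section 9.4.3 calls all secondary analyses exploratory.

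**The concern.** The rule fixes the date at the first positive answer and ignores everything after it. A patient who says 'Yes' in week 3 and 'No' in weeks 4 to 9 is analysed as healed at 3 weeks. So is a patient who says 'Yes' in week 3 and is later given rescue for an unhealed wound. In the second case the trial's own database would contradict the analysed value.

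Healing time is a named secondary objective and one of the benefits the sponsor hopes to see with the xenograft (section 2.2). It will be reported with a test, an estimate and an interval. If reversals occur and no rule is written down, the choice between conflicting answers may be made after the data are seen. If they are more frequent in one arm, the comparison is distorted.

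**Working it through.** **The plan's figures.** The plan gives no healing-time distribution, no rate of mistaken answers and no sample size for this endpoint. Its only sizing is for POSAS: 38 by t-test, 38/0.864 = 43.98, so 44, and 44/0.9 = 48.9, rounded up to 50 in equal arms. This reproduces but has no bearing here, except that 44/2 = 22 per arm is used below.

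**Direction.** Let F be the week of the first 'Yes' and S the week of the first 'Yes' with no later 'No'. S is itself a 'Yes' week, so F ≤ S always, with equality when no 'No' follows F. An override by a later finding of an open wound can only move the date later again.

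**Hypothetical patients under the two rules:**

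| Record | First 'Yes' | Sustained 'Yes' with override |
|---|---|---|
| 'Yes' wk 3, 'No' wk 4–9, 'Yes' wk 10–12 | 3 | 10 |
| 'Yes' wk 3–12; rescue for an unhealed wound in wk 10 | 3 | 11 |
| 'Yes' wk 6–12; wound open at a visit in wk 13 | 6 | not healed by wk 12 |
| 'Yes' wk 5–12; true closure wk 8; closed at visit | 5 | 5 (not corrected) |
| True closure wk 5; one mistaken 'No' in wk 8 | 5 | 9 (too late) |

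**Illustration 1: isolated errors.** Assume closure at week 8 and an independent chance f of a false 'Yes' in each of the 7 open weeks.

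- First 'Yes': P(too early) = 1 − (1 − f)^7; mean recorded week = [1 − (1 − f)^8]/f.
- Sustained 'Yes': a too-early date needs a false 'Yes' in week 7, so P(too early) = f; mean = 8 − (f + f² + … + f^7).

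| f (assumed) | First 'Yes': too early, mean week | Sustained: too early, mean week |
|---|---|---|
| 0.02 | 13%, 7.46 | 2%, 7.98 |
| 0.05 | 30%, 6.73 | 5%, 7.95 |
| 0.10 | 52%, 5.70 | 10%, 7.89 |

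**What this does to the arm comparison.** Simulation: 22 per arm, 4000 runs, equal true healing (mean 8, SD 2 weeks), Mann-Whitney at .05.

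- Equal error (f = 0.05 in both arms): rejection about 4% under either rule.
- Error placed in one arm only (f = 0.02, 0.05, 0.10): about 10%, 33%, 81% under first 'Yes'; about 4%, 4%, 6% under the sustained rule.

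The second line follows from putting all the error in one arm. It shows what would be needed, not what is expected.

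**Illustration 2: persistent errors.** Assume instead true healing Normal(8, 2.5), and that a share of one arm answers 'Yes' some weeks early and keeps doing so. Later answers then correct nothing. Only P(Z > (13 − 8)/2.5) = P(Z > 2), about 2%, of wounds are still open at week 13 to be caught by a visit. Rejection under first 'Yes' and under the sustained rule with override (22 per arm, 3000 runs):

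- 20% of patients 3 weeks early: 9.6% and 9.5%
- 30% of patients 3 weeks early: 18.2% and 17.9%
- 40% of patients 4 weeks early: 39.5% and 38.7%

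The fix therefore works on answers that are reversed or contradicted, and hardly at all on persistent ones.

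**The case against.** The sponsor can fairly say that the endpoint is declared patient-based, subjective and exploratory, and that the reason for not measuring it objectively is stated. The question itself defines healed as closed with no open areas. Both arms are told to redress the wound and apply petroleum jelly every day until it heals, so patients see the site. Nothing in the documents suggests that reversals are common. All of that stands, and it limits the weight of the point. It does not close the gap: the feasibility argument concerns new measurements, whereas the later weekly answers, the rescue date and the 3-month visit are already planned.

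A reader might go further and infer that the rule favours the xenograft, because a graft adhering to the wound hides open areas. The documents do not support this. Section 2.2 says that "porcine xenografts afford longer wound adherence", but the sentence compares the product with other biosynthetic dressings and says nothing about how patients judge closure. A graft still in place could equally lead a patient to keep answering 'No', which would work against the xenograft. A reader might also take the simulated rejection rates as the false-positive rate of this trial. They are not: they depend on assumed errors confined to one arm, and the inflation vanishes when the errors are equal.

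**Conclusion.** The point holds in a limited form. As written, a 'Yes' that is later reversed, or contradicted by a rescue record for an unhealed wound or by an open wound at the visit, still counts as healing at the early week. Relative to a sustained-'Yes' rule the recorded week can only be equal or earlier. That much follows from the text alone.

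Whether it produces a spurious difference between arms depends on errors differing by arm. Lack of patient blinding makes that possible, but no document gives an error rate or establishes a direction. The size is therefore unknown, and the figures above rest on assumed healing times and error rates.

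This is a worthwhile, inexpensive improvement to an exploratory secondary endpoint. The blinded primary endpoint, the sample size and the safety analyses are untouched.

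**What to change.** In sections 3 and 9.4.3:

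1. Define healing time as the week of the first 'Yes' with no later 'No' through week 12.
2. Where a rescue record for an unhealed wound, or the 3-month visit, shows the wound open after a reported 'Yes', discard that 'Yes' and use the first later sustained 'Yes'.
3. If there is none by week 12, rank the patient as not healed by week 12, tied above all observed healing times in the Mann-Whitney test. Any code above 12, such as 13, gives the same ranks. The mean, and possibly the Hodges-Lehmann estimate, depend on the code, so state it and give the number of such patients by arm.
4. Keep the first-'Yes' version as a sensitivity analysis, and report reversals and overrides by arm.

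The cost is wording; no visit or sample size changes. Section 6.5.1 lists the date, time, name and regimen of rescue but not wound status. If open or closed is not already recorded at rescue and at the 3-month visit, one yes/no item is needed.

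There are two downsides. A mistaken later 'No' lengthens one patient's time, which the sensitivity analysis will show. A persistent false 'Yes' on a wound that closes before the visit stays uncorrected, and a single visit at 2 to 4 months can refute a 'Yes' but cannot date closure.

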1.2 SCHEMA

1.3 SCHEDULE OF ACTIVITIES (SOA)

Procedures	Screening	Enrollment/Surgery Visit 1	3-Month after surgery- Weekly Questionnaires	3 month follow-up visit ±1 month after surgery date
Informed consent	Х			
Demographics	Х			
Medical history	Х			
Randomization	Х			
Administer study intervention		Х		
Physical exam (including height and weight)	х	Х		х
Vital signs	Х	Х		Х
Height	Х	Х		Х
Weight	Х	Х		Х
Performance status	Х	Х		Х
Hematology				
serum chemistry ^a				
Pregnancy test ^b				
EKG (as indicated)				
Adverse event review and evaluation	Х			
Complete Case Report Forms (CRFs)	х	Х	Х	х
Questionnaire reporting			Х	
Blinded Wound/Scar Assessment				х

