6.3 MEASURES TO MINIMIZE BIAS: RANDOMIZATION AND BLINDING

A randomization schedule will be generated by the Biostatistics Unit at the Feinstein Institute for Medical Research to assign a repair method (porcine xenograft placement or second intention healing). Block randomization will be used to ensure balance in the number of patients allocated to each treatment group. The allocation ratio will be 1:1. The randomization schedule will be uploaded to REDCap by a statistician outside of the study team. The PI, who will screen eligible subjects, will not have user rights for the Randomization Setup module within REDCap, and will thus be blinded to which treatment arm is next on the randomization list. The PI will use the "Randomize" button within REDCap to assign patients to porcine xenograft or second intention healing as they are enrolled.

There will be one physician who will perform all of the surgical procedures, which will remove bias in technique. There will additionally be two blinded physicians who will be tasked with observing the scar and assessing the primary efficacy endpoint (POSAS observer scale total score). The study statistician will be blinded to the treatment groups in order to avoid bias or the appearance of bias. All data provided to the statistician will list the treatment group as "A" or "B".

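### The initial defect size, the denominator of the scar-to-defect ratio, need not be recorded before randomization, so it can be measured by someone who knows the arm

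*Combined protocol and SAP*

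**What the plan says.** The third secondary endpoint (Sections 3 and 9.4.3) is scar area at the 3-month visit divided by initial defect area, each area being length times width.

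- **Denominator.** Section 9.4.3: "The initial postoperative defect size will be measured by the investigator prior to intervention in terms of length and width using a sterile ruler". Sections 4.1, 6.1.1 and 8.1 also time this reading against the intervention and not against randomization.
- **Numerator.** Section 9.4.3: "Scar size will be measured in terms of length and width at the 3-month follow-up visit". No measurer is named in that sentence.
- **Label.** Section 9.4.3: "The ratio of scar size to initial defect size is an objective endpoints". Section 3 says the same.
- **Randomization.** Sections 4.1 and 6.3 have the PI assign the arm with the REDCap Randomize button; 4.1 adds that this follows consent and enrolment. The Schedule of Activities (1.3) ticks it under Screening, one column ahead of the surgery visit. The Synopsis (1.1) and Background (2.2) place it once surgery is finished.
- **Blinding of the scar assessment.** Section 4.1: "Assessment of the scar will be blinded in nature". The scar row at the 3-month visit in 1.3 is headed "Blinded Wound/Scar Assessment".

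**The concern.** Where the edge of a fresh wound lies is partly a judgement, even with a ruler. If the person measuring already knows the arm, the reading can drift with expectation. The plan states that expectation: Section 2.2 anticipates smaller scars with xenograft. Over-reading the defect in the xenograft arm lowers that arm's ratio, which is the hoped-for direction.

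The ratio also carries particular weight among the secondary endpoints. The other four are patient-reported and patients cannot be blinded, so this is the only secondary efficacy endpoint that blinding can protect. It is also the only efficacy endpoint that the plan describes as objective. It will be tested at the .05 level and reported with a 95% confidence interval (9.4.1, 9.4.3).

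**Working it through.** **1. Who can know the arm.** The PI learns it on pressing Randomize (4.1, 6.3). The single operating physician (6.3) must know it in order to apply it. Section 9.4.3 gives the defect reading to the investigator without saying which one. Whoever that is, a reading taken after assignment has no protection against knowledge of the arm.

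**2. Whether the order is fixed.**
- On the order in 1.3 (randomization at Screening, then surgery), no post-operative defect exists at assignment. Every defect would be measured afterwards.
- On the order in 1.1 and 2.2 (surgery, then randomization), the reading may fall on either side of assignment, because it is tied only to the start of the intervention.
- The Schedule of Activities has no row for defect measurement that could settle this.

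**3. Whether eligibility closes the gap.** Section 5 requires a post-operative defect above 8 mm in greatest diameter or length, so some sizing should precede enrolment. That check concerns one dimension against a threshold. Nothing says that the recorded length and width are taken at that moment.

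**4. Size.** The plan gives no expected defect size, scar size or reading error, so the figures below are illustrations on assumed errors. The ratio is R = (scar length x width) / (defect length x width). If each defect dimension is multiplied by (1 + b), R is multiplied by 1/(1 + b)^2.
- 8 x 8 mm read as 9 x 9 mm: 64/81 = 0.79.
- 20 x 20 mm read as 21 x 21 mm (b = 1/20 = 0.05): 400/441 = 0.91.

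**5. Effect on the test.** Section 9.2 gives a total of 38 by t-test, then 38/0.864 = 43.98, so 44, then 50 after 10% attrition. These figures reproduce: 2 x (1.96 + 0.84)^2 x 6.5^2/6^2 = 18.4, so 19 per arm and 38 in total; and 44/0.9 = 48.9, so 49, which becomes 50 as an even total. They concern the primary endpoint and serve here only to give 44/2 = 22 evaluable patients per arm. A simulation then assumed no true effect, a lognormal ratio, every defect in one arm over-read by 5% per dimension and none in the other, and a two-sided Mann-Whitney test at .05, with 4,000 trials per row:

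| Assumed log-SD of the ratio | Rejections, no error | Rejections, 5% defect over-reading in one arm |
|---|---|---|
| 0.3 | 5.4% | 18.7% |
| 0.5 | 5.4% | 10.1% |
| 0.7 | 4.9% | 7.6% |

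**The case against.** **On the denominator.** The Synopsis and Background both put randomization after surgery, eligibility depends on the size of the post-operative defect, and consultation and surgery often fall on the same day (5.4). The Screening column may therefore reflect only the layout of the schedule, and the defect may in practice be measured first. That is plausible, but no section requires it, and 1.3 read literally makes it impossible. This part of the objection narrows the concern without removing it.

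**On the numerator.** A reader might infer that the scar is measured unblinded. Section 4.1 says that the scars are measured and "two blinded investigators will then assess the scar for the primary efficacy endpoint at this time", and 6.3 refers to "two blinded physicians who will be tasked with observing the scar and assessing the primary efficacy endpoint", with no mention of a ruler. The documents do not support that inference. Section 4.1 and the schedule both describe the scar assessment as blinded. Section 8.1 repeats the sentence from 4.1 without limiting the evaluators' task to the primary endpoint. In both 4.1 and 8.1 the ruler sentence closes the paragraph about the blinded evaluators. Blinded measurement is the natural reading; it is merely not assigned in so many words. Section 6.5.1 likewise names no measurer for the later visits of patients who receive rescue medication.

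**On size.** A reader might take the area arithmetic as evidence of bias. It shows only sensitivity. Error common to both arms does not favour either one, and nothing in the documents indicates that errors differ by arm or by how much. Nor is 8 x 8 mm the smallest eligible wound: the criterion concerns the greatest dimension, so narrower ovals qualify. Relative error in area is about twice that in each dimension only when both dimensions err the same way; independent errors of equal relative size combine to about 1.4 times (the square root of 2).

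**On the label.** Calling a ruler measurement objective, in contrast to rating scales, is defensible and changes no analysis. It does make an unprotected denominator easier to overlook.

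**Conclusion.** The concern holds for the denominator. As written, the plan allows the recorded defect size to be measured with the arm known, and its sections disagree on whether randomization comes before or after surgery. It does not establish that this will happen, that any bias will follow, or that the scar itself is measured unblinded.

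Under the assumed errors, the ratio in one arm would be multiplied by 0.79 (1 mm per dimension at 8 x 8 mm) or 0.91 (1 mm at 20 x 20 mm). A consistent one-arm over-reading of 5% per dimension would raise false positives from about 5% to between 8% and 19%, depending on the assumed spread of the ratio. All of this requires errors that differ by arm.

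The consequence is limited. Section 9.4.3 treats every secondary endpoint as exploratory, and neither the primary endpoint nor the sample size is touched. The change is worth making because it removes the problem at no cost.

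**What to change.** 1. In 4.1 and 9.4.3, and in the matching sentences of 6.1.1 and 8.1, state: *Defect length and width are measured after completion of surgery and entered in REDCap before the Randomize button is used.*
2. Reconcile 1.1, 1.3 and 2.2 so that randomization follows completion of surgery and defect measurement, and add a defect-measurement row to the schedule.
3. As a clarification only, state in 9.4.3 that the blinded evaluators measure scar length and width, including at the later visits described in 6.5.1. One blinded reading is enough. If both evaluators measure, say how the readings are combined; averaging two readings is optional.

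The cost is a text amendment with IRB approval. The ruler reading is already planned and only has to precede a button press, and the evaluators already attend the 3-month visit. Sample size and analysis do not change.
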